#### **8.4.10 Abuse, Misuse, Overdose, and Medication Error**

Abuse, misuse, overdose, or medication error should not be reported per the SAE reporting procedure. Only a resulting AE, if it occurs, should be reported according to the procedures as described in Section 10.4. All IP provided to pediatric participants should be supervised by the parent(s)/caregiver(s)/LAR(s).

The definitions below are not mutually exclusive; an event can meet more than 1 category.

- **Abuse:** Persistent or sporadic intentional intake of an IP for a nonmedical purpose (eg, to alter one's state of consciousness or get high) in a manner that may be detrimental to the individual and/or society.
- **Misuse:** Intentional use of an IP other than as directed or indicated at any dose. (Note: This includes a situation in which the IP is not used as directed at the dose prescribed by the protocol.)
- **Overdose:** Intentional or unintentional intake of a dose of an IP exceeding a prespecified total daily dose of the product.
- **Medication error:** An error made in prescribing, dispensing, administering, and/or use of an IP. For studies, medication errors are reportable to the sponsor only as defined below.
  - Cases of participant's missing doses of the IP are not considered reportable as medication errors.
  - Medication errors should be collected and reported for the IP under investigation.
  - The administration and/or use of an expired IP should be considered as a reportable medication error.

#### **8.5 Treatment of Overdose**

For this study, any dose of GNX greater than up to 63 mg/kg/day or over the maximum of 1800 mg/day (900 mg/day) within a 24-hour time period will be considered an overdose.

Sponsor does not recommend specific treatment for an overdose, but participants should be closely monitored and receive supportive care.

In the event of an overdose, the investigator should:

- Contact the medical monitor immediately.
- Evaluate the participant to determine, in consultation with the medical monitor, whether study intervention should be interrupted or whether the dose should be reduced.
- Closely monitor the participant for any AE/SAE and provide any appropriate supportive medical management.
- Obtain a plasma sample for PK analysis within 1 day from the date of the last dose of study intervention if requested by the medical monitor (determined on a case-by-case basis).
- Document the quantity of the excess dose as well as the duration of the overdose in the eCRF.

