#### **4.3 Justification for Dose**

A minimum GNX dose of 33 mg/kg/day or 900 mg/day is generally required for assessment of efficacy during the study. Clinical studies have demonstrated that GNX has anticonvulsant activity with an acceptable safety and tolerability profile in the dose range of 900 to 1800 mg in adults and children (Sperling et al, 2017; Laxer et al, 2000; Kerrigan et al, 2000; Pieribone et al, 2007).

Dosing will be based on doses that have been shown to be safe in children and adults in multiple studies with healthy volunteers and individuals with epilepsy.

In both parent studies (Study 1042-TSC-3001 and Study 1042-TSC-2001), GNX is to be titrated to a maximum target dose of 1800 mg/day and given as an oral suspension (50 mg/mL) with food, eg, shortly after a meal or snack.

Participants will continue the GNX dose determined in Study 1042-TSC-3001 or Study 1042-TSC-2001 in this OLE unless a dose change is clinically indicated.

Additional dosing information can be found in Section 6.2.

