## 7.2 Discontinuation/Withdrawal from the Study

All participants or his/her parent(s)/LAR(s) reserve the right to withdraw from the study at any time, as stated in the informed consent/assent form. The investigator may discontinue participants from the clinical study for any of the following reasons:

- Participant is found to have entered the study in violation of the protocol.
- Participant requires the use of a disallowed concomitant medication.
- Participant's condition changes after entering the clinical investigation so that the participant no longer meets the inclusion criteria or develops any of the exclusion criteria.
- Participant or parent(s)/LAR(s) withdraws consent or assent to participate in the study.
- Participant is noncompliant with the procedures set forth in the protocol.
- Participant experiences an AE/SAE that warrants withdrawal from the study.
- Any laboratory, medical, or clinical finding for which clinical intervention should take precedence over study participation. This includes:
  - Aspartate aminotransferase (AST)/serum glutamic oxaloacetic transaminase (SGOT) or alanine aminotransferase (ALT)/serum glutamic pyruvic transaminase (SGPT)  $> 3 \times$  upper limit of normal (ULN).
  - Total bilirubin levels  $> 1.5 \times$  ULN.
  - Estimated glomerular filtration rate (eGFR)  $< 30$  mL/min.
- It is the investigator's opinion that it is not in the participant's best interest to continue in the study.

Decisions to discontinue the study will be made at each participating site by the investigator. If feasible, the reason for discontinuation should be discussed with the sponsor's medical monitor prior to participant's discontinuation.

At the time of discontinuing from the study, if possible, an Early Termination Visit (Visit 13 [Week 156]) should be conducted as shown in the SOA (Table 1). At this visit, participants will start a 2-week taper and then return to the site 2 weeks later for safety follow-up assessments.

If the participant withdraws consent for disclosure of future information, the sponsor may retain and continue to use any data collected before such a withdrawal of consent.

If a participant withdraws from the study, he/she may request destruction of any samples taken and not tested, and the investigator must document this in the site study records.

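### The overdose sentence in Protocol 8.5 is garbled by an unexplained 900 mg/day, and 7.2 leaves optional two laboratory stops that 8.3.4 makes mandatory

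*Protocol*

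**What the plan says.** **Overdose.** Protocol 8.4.10 defines overdose as "Intentional or unintentional intake of a dose of an IP exceeding a prespecified total daily dose of the product", without a figure. Protocol 8.5 supplies one. Its threshold begins "any dose of GNX greater than up to 63 mg/kg/day" and continues with a dose "over the maximum of 1800 mg/day (900 mg/day) within a 24-hour time period will be considered an overdose". Section 6.2 (in the dose-reduction bullets) and section 9.2.5 both give the maximum daily dose as 63 mg/kg or 1800 mg, with no mention of 900.

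Section 4.3 places 900 mg/day at the other end of the scale: "A minimum GNX dose of 33 mg/kg/day or 900 mg/day is generally required for assessment of efficacy during the study". It is also the bottom of the range described as having an "acceptable safety and tolerability profile in the dose range of 900 to 1800 mg in adults and children". On the parent studies the same section says that "GNX is to be titrated to a maximum target dose of 1800 mg/day".

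**Laboratory stopping.** Protocol 7.2 opens its list with "The investigator may discontinue participants from the clinical study for any of the following reasons". Under the bullet on findings that should take precedence over participation it names AST or ALT above 3 x ULN, total bilirubin above 1.5 x ULN and eGFR below 30 mL/min. It adds that the site investigator makes decisions to discontinue. Protocol 8.3.4 says that a participant whose bilirubin rises to 1.5 x ULN or more, or whose eGFR is below 30 mL/min post baseline, *will* be discontinued.

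**The concern.** An overdose under 8.5 sets off specific actions: immediate contact with the medical monitor, a decision on interrupting or reducing the dose, close monitoring, and an eCRF record of the size and duration of the excess. The excess cannot be recorded consistently if the sentence that fixes the limit contains a second, unexplained number.

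Reporting is affected only at the edge. Section 8.4.10 says "Abuse, misuse, overdose, or medication error should not be reported per the SAE reporting procedure", so normally only a resulting adverse event is reported. Section 10.4.1 makes one exception: an intentional overdose with possible suicidal or self-harming intent is reported whatever its consequences.

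On laboratory stopping, a site that follows 8.3.4 breaches nothing in 7.2. A site that consults only 7.2, the section on discontinuation from the study, could keep a participant whom 8.3.4 requires to be stopped. Safety is the primary objective, and the study runs for up to about 3 years at about 75 sites, so both rules should be readable without inference.

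**Working it through.** No sample size, power or error-rate figure is involved. The check compares the sections and uses simple arithmetic on the dose limits.

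**1. The intended dose limit.** Inputs: 63 mg/kg/day and 1800 mg/day (6.2, 9.2.5); 900 mg/day (8.5, 4.3); 33 mg/kg/day (4.3).

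Permitted maximum = the lower of 63 x weight and 1800 mg/day. The two limits meet at 1800/63 = 28.6 kg. With the 900 removed, 8.5 gives the same limit as 6.2 and 9.2.5.

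**2. Could 900 mg/day be a real overdose limit?** Suppose, hypothetically, that it were.

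- It would fall below the permitted maximum for anyone above 900/63 = 14.3 kg.
- The efficacy minimum of 33 mg/kg/day reaches 900 mg/day at 900/33 = 27.3 kg. This assumes that the lower of the two figures in 4.3 is the minimum that applies. Above that weight, the usual efficacy minimum and the overdose limit would be the same dose.
- The 1800 mg/day parent-study target would be 1800/900 = 2.0 times the limit.

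| Weight (kg) | Permitted maximum (mg/day) | Efficacy minimum (mg/day) | Is the permitted maximum above 900? |
|---|---|---|---|
| 10 | 63 x 10 = 630 | 33 x 10 = 330 | no |
| 20 | 63 x 20 = 1260 | 33 x 20 = 660 | yes |
| 28 | 63 x 28 = 1764 | 900 | yes |
| 40 | 1800 | 900 | yes |

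The weights are illustrative. A 900 mg/day limit is incompatible with the dosing that 4.3 and 6.2 allow, so it cannot be a general overdose limit. The table shows this incompatibility. It does not predict what sites will do.

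**3. The laboratory rules side by side.**

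| Finding | 7.2 | 8.3.4 |
|---|---|---|
| Total bilirubin | above 1.5 x ULN: *may* | 1.5 x ULN or more: *will* |
| eGFR | below 30 mL/min: *may* | below 30 mL/min post baseline: *will* |
| AST or ALT | above 3 x ULN: *may* | above 3 x ULN: weekly retest, continue if falling; *will* if not back under 3 x ULN |

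For eGFR the cut-off is identical and only the required action differs. For bilirubin the cut-offs differ only at exactly 1.5 x ULN, so the action is again what matters. For AST/ALT, an option to stop at once does not contradict the retest rule. Section 8.3.4 does not say whether discontinuation is from the product or from the study, while 7.2 concerns the study. That is a further ambiguity and does not remove the conflict.

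**The case against.** The strongest reply is that neither defect would mislead a careful site. The operative words of 8.5 point to 1800 mg/day; 6.2 and 9.2.5 give the full limit; and participants arrive on doses titrated to as much as 1800 mg/day in the parent studies. A site that mistook 900 for a ceiling would have to call the medical monitor immediately, and would probably be corrected. On stopping, both sections can be obeyed together. The *may* list in 7.2 is a general authority clause that also covers withdrawal of consent, 8.3.4 is the specific rule, and section 8 treats adherence to the study requirements as essential.

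Much of this stands. It rules out several stronger readings that a reader might reach for:

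- *That overdose is set at 900 mg/day, so that permitted doses count as overdoses.* The documents do not support this; the 900 is probably a drafting remnant.
- *That the two sections use different renal thresholds.* They do not.
- *That AST/ALT is in conflict too.* Section 8.3.4 does not contradict the discretionary option in 7.2.
- *That the flat 1800 mg/day in the Synopsis, 4.1 and the end of 6.2 is an error.* It is a true absolute ceiling; it only leaves out the weight-based limit.
- *That the analysis is compromised.* SAP 4.3.1 and 5.7 plan no overdose summary.

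What remains is that a site should not have to reconstruct an operative safety threshold from other sections, or work out which of two verbs governs a mandatory stop.

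**Conclusion.** The point holds as a defect of wording in two safety rules. The overdose sentence in 8.5 is garbled, although its intended limit of 63 mg/kg/day or 1800 mg/day can be recovered from 6.2 and 9.2.5. Discontinuation for bilirubin and eGFR is discretionary in 7.2 and mandatory in 8.3.4. The consequences lie in site conduct: medical-monitor contact, dose decisions, eCRF recording and stopping. The documents give no basis for counting affected participants, and no statistical figure in the plan changes.

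The conclusion assumes that the 900 mg/day has no intended meaning, which only the sponsor can confirm, and that 8.3.4, as the specific laboratory rule, is meant to govern. The correction should be made: it is cheap and both rules are operative.

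**What to change.** 1. **Section 8.5.** Once the sponsor's medical team confirms that the 900 mg/day has no intended meaning, replace the threshold with: *any total daily dose of GNX above the lower of 63 mg/kg/day and 1800 mg/day within a 24-hour period will be considered an overdose.*
2. **Section 7.2.** Keep AST/ALT above 3 x ULN as a discretionary reason, so that the investigator retains the explicit option to stop without waiting for retests. Replace the bilirubin and eGFR sub-bullets with a separate sentence: *Participants with total bilirubin of 1.5 x ULN or more, or eGFR < 30 mL/min post baseline, will be discontinued as stated in Section 8.3.4.* Begin the sentence on investigator decisions with *Except where Section 8.3.4 requires discontinuation*.
3. **Optional tidying.** Add the 63 mg/kg/day limit to the Synopsis, 4.1 and the end of 6.2. Say in 8.3.4 whether discontinuation is from the product or from the study.

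The cost is wording in the next protocol amendment, with its usual IRB/IEC approval, and health authority approval if the amendment is substantial, across about 75 sites. It needs no new data, procedures or analyses.

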## **8.6 Pharmacokinetics and Pharmacodynamics**

### **8.6.1 Pharmacokinetics**

Whole blood samples of approximately 2 mL will be collected for measurement of the plasma concentrations of GNX as specified in the SOA (Section 1.3).

There is no specified time window for collection of the blood sample for PK analyses.

The time of the participants' last dose of the IP and the time of their next dose of the IP should be specified in relation to the time of the PK draw.

The actual date and time (24-hour clock time) each sample is collected must be accurately recorded in the source document and appropriate eCRF.

Instructions for the collection and handling of biological samples will be provided by the sponsor. Please refer to the laboratory manual for processing instructions.

Samples will be used to evaluate the PK of GNX. Each sample will be divided into 2 aliquots (1 for PK, 1 as a backup). Samples collected for analyses of GNX concentration may also be used to evaluate safety or efficacy aspects related to concerns arising during or after the study.

Additional samples may be collected at additional timepoints during the study if warranted and agreed upon between the investigator and the sponsor. The timing of sampling may be altered during the course of the study based on newly available data (eg, to obtain data closer to the time of peak plasma concentrations) to ensure appropriate monitoring.

### **8.6.2 Pharmacodynamics**

PD parameters are not evaluated in this study.

## **8.7 Genetics**

Genetic parameters are not evaluated in this study.

## 8.8 Biomarkers

Biomarkers are not evaluated in this study.

## 8.9 Immunogenicity Assessments

Immunogenicity is not evaluated in this study.

## 8.10 Health Economics

Health economics are not evaluated in this study.

# 9 STATISTICAL CONSIDERATIONS

The statistical analysis plan (SAP) will be finalized prior to database lock and it will include a more technical and detailed description of the statistical analyses described in this section. This section is a summary of the planned statistical analyses of the most important endpoints including primary and key secondary endpoints.

All statistical analyses will be performed using SAS® (SAS Institute, Cary, NC 27513) software.

## 9.1 Analysis Sets

For the purposes of analysis, the following analysis sets are defined:

Participant Analysis Set	Description
Intent-to-treat (ITT) set	All participants who receive at least 1 dose of the IP. Participants will be summarized overall and by the treatment group to which they were randomized in the parent study (placebo or GNX). This population will be used for efficacy analyses.
Safety analysis set	All participants who receive at least 1 dose of the IP. This population will be used for the safety analyses.

GNX = ganaxolone; IP = investigational product/GNX.

The intent-to-treat (ITT) analysis set is used to analyze endpoints related to the efficacy objectives and the safety analysis set is used to analyze the endpoints and assessments related to safety. The efficacy analyses will be performed within the ITT population.

## 9.2 Statistical Analyses

### 9.2.1 General Considerations

The results of the primary, secondary, and exploratory endpoints will be summarized separately. The results will be summarized by the treatment received by participants in the parent study. Participant demographics, characteristics, and medical history at randomization or the start of the parent study will be summarized using descriptive statistics.

### **9.2.2 Primary Endpoints**

The primary endpoints are the following safety endpoints:

- Incidence and severity of AEs, SAEs and withdrawals and dose-reductions due to AEs.
- Vital sign measurements including BP, HR, RR, body temperature, height, and body weight.
- Physical, neurological, and developmental examination.
- 12-lead ECG.
- Clinical laboratory tests.
- C-SSRS.

Further details are provided in Section 9.2.5.

### **9.2.3 Secondary Endpoints Analysis**

The secondary endpoints are:

- Percentage change from baseline in 28-day seizure frequency during open-label treatment (first year only).
- Percentage change from baseline in 28-day seizure frequency during the long-term treatment (first year only).
- Number (%) of participants considered treatment responders (first year only).
- CGI-I at the last scheduled study visit.
- Change from baseline in the quality-of-life scale SF-36 (first year only).
- Change from baseline in the percentage of seizure-free days during treatment, based on seizure type (first year only).
- Change from baseline of CGI-CSID.

All the endpoints will be included in data listings.

### **9.2.4 Pharmacokinetic Analysis**

A population PK approach addressing the relationship between GNX PK parameters and individual characteristics will be implemented as follows:

- Visit 3 (Week 26).
- Visit 5 (Week 52).

For PK assays there is no specified time to draw the PK sample and these can be drawn whenever convenient during the specified study visits.

Exact time of sample withdrawal and drug intake will be recorded in the eCRF.

### **9.2.5 Safety Analyses**

All safety analyses will be performed in the Safety Population. The results will be summarized overall and by the treatment received in the parent study (placebo or GNX).

The number and percentage of days participants received IP, the highest percentage of the maximum allowable daily dose (1800 mg or 63 mg/kg) participants received, and the total amount of IP received will be summarized.

A participant data listing will be provided with full details of the study drug dispensation.

Safety assessments include:

- AEs.
- Vital signs including BP, HR, RR, body temperature, height, and body weight.
- Physical, neurological, and developmental examinations.
- 12-lead ECG.
- Clinical laboratory tests.
- Concomitant ASM levels (as detailed in Section 8.3.6).
- C-SSRS.

Detailed analysis and complete listings will be outlined in the SAP.

### **9.2.6 Subgroup Analysis**

The following subgroup summarizations of the efficacy parameter are planned as outlined in the SAP:

- Gender (Female vs Male).
- Age groups (1 to 6 years; 7 to 12 years; 13 to 17 years; and 18 years and above).

All the analyses will follow the rules:

- The results will be presented overall, for participants previously enrolled in Study 1042-TSC-2001, and for participants previously enrolled in Study 1042-TSC-3001 results will also be classified according to the double-blind treatment received by participants in Study 1042-TSC-3001.
- The seizure endpoints will be derived starting from the first dosing day of OLE treatment.
- No per protocol analyses will be performed

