### 3 OBJECTIVES AND ENDPOINTS

Objectives	
Primary Objective	

• To assess the long-term safety and tolerability of GNX as adjunctive therapy for seizures associated with TSC in children and adults.

	
Secondary Objectives	

• For the first year, to determine the percentage of change from baselinea in 28-day seizureb frequency during open-label treatment.

• For the first year, to assess the change in frequency of countable focal seizures frequency from baselinea during open-label treatment.

• For the first year, to assess changes in mood, behavior, and quality of life using SF-36.

• To assess overall clinical outcome using CGI-I scores by the clinician and the parent(s)/caregiver(s)/LAR(s).

• To evaluate the changes in seizure intensity and duration using the CGI-CSID.

	
Exploratory Objectives	

• To evaluate the long-term effects of GNX as add-on therapy to antiepileptic medications.

	
Endpoints	
Primary Endpoints	
The primary endpoints are the following safety endpoints:	

• Incidence and severity of AEs, SAEs and withdrawals and dose-reductions due to AEs.

• Vital sign measurements including blood pressure, heart rate, respiratory rate, body temperature, height, and body weight.

• Physical, neurological, and developmental examination.

• 12-lead ECG.

• Clinical laboratory tests.

• C-SSRS.

	
Secondary Endpoints	

• Percentage change from baselinea in 28-day seizureb frequency during open-label treatment (first year only).

• Percentage change from baselinea in 28-day seizureb frequency during the long-term treatment (first year only).

• Number (%) of participants considered treatment respondersc (first year only).

• CGI-I at the last scheduled study visit.

• Change from baseline in the quality-of-life scale SF-36 (first year only).

• Change from baselinea in the percentage of seizure-free days during treatment, based on seizure typeb (first year only).

• Change from baseline of CGI-CSID.

	

---

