### **2.2. Study Objectives**

#### **2.2.1. Primary Objective**

The primary objective of the study is: to assess the long-term safety and tolerability of GNX as adjunctive therapy for seizures associated with TSC in children and adults.

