### 4.3. Statistical Methods for Primary Safety Analyses

#### 4.3.1. Adverse Events

Adverse events (AEs) are collected from the time of informed consent/assent through the defined follow-up period. AEs are coded using MedDRA dictionary, version 24.0 and are

categorized by system organ class (SOC) and preferred term (PT). A treatment-emergent AE (TEAE) is defined as an AE that starts or worsens on or after the first day of dosing with IP. Detailed by-patient listings of all AEs reported during the study will be provided and will include verbatim and coded terms for each AE.

For the safety Analysis Set, the following tabular summaries will be created:

- An overall summary of TEAEs will present the number and percentage of subjects with at least 1 reported TEAE, study drug related TEAE, serious TEAE, TEAE of Grade 3 or higher, study drug infusion interruption, and death
- TEAEs by system organ class and preferred term
- TEAEs by system organ class, preferred term, and maximum severity
- Study drug related TEAEs by system organ class and preferred term
- TEAEs by decreasing frequency of preferred term
- Moderate or severe TEAEs by system organ class and preferred term
- Moderate or severe study drug related TEAEs by system organ class and preferred term
- TEAEs that led to study drug infusion interruption by system organ class and preferred term
- Serious TEAEs by system organ class and preferred term
- Serious study drug related TEAEs by system organ class and preferred term

For incidence reporting, if a subject reported more than 1 AE that was coded to the same preferred term/system organ class, the subject will be counted only once for that specific preferred term/system organ class. For TEAEs presented by severity, the worst severity for each event during the clinical trial will be presented for each subject. If the severity is missing for a TEAE, then a severity of “Severe” will be assigned. The imputed values for severity assessment will be used for incidence summaries, while the actual values will be used in data listings.

For TEAEs presented by relationship to study drug, the closest relationship to study drug for each event during the clinical trial will be presented for each subject. If the relationship to investigational product is missing for a TEAE, a causality of “Related” will be assigned. The imputed values for relationship assessment will be used for incidence summaries, while the actual values will be presented in data listings.

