#### 4.3.5. Columbia-Suicide Severity Rating Scale (C-SSRS)

The Columbia-Suicide Severity Rating Scale (C-SSRS) is a patient questionnaire that evaluates suicidal ideation and behaviors. The results (yes/no) from the 5 questions under suicidal ideation and the 5 questions under suicidal behavior will be summarized at baseline and post baseline using percentages and counts. The denominator for percentages will be the number of subjects with a C-SSRS assessment at baseline or at any time post baseline. The post-baseline by-question summary will list a subject as "yes" if they selected yes at any time after baseline.

The C-SSRS suicidal behavior and suicidal ideation scores recorded at baseline and any changes in post-baseline scores from the previous visit will be summarized descriptively by visit, including the number and percentage of subjects reporting any suicidal behavior and any suicidal ideation as defined in **Table 1**. Adult and pediatric C-SSRS data will be summarized separately.

C-SSRS data collected, including scores for suicidal ideation, intensity of ideation and actual suicide attempts, will be listed by patient and visit.

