## 4.4. Statistical Methods for Secondary Efficacy Analyses

### 4.4.1. Percentage change from baseline in 28-day seizure frequency during open-label treatment.

Seizure types are defined as the following: focal motor seizures without impairment of consciousness or awareness, focal seizures with impairment of consciousness or awareness with motor features, focal seizures evolving to bilateral, tonic-clonic convulsive seizures, and generalized motor seizures including tonic-clonic, bilateral tonic, bilateral clonic, or atonic/drop seizures. Seizures must have a motor component sufficiently prominent and distinct to clearly establish the observed symptoms as epileptic in origin. Seizures that do not count towards the efficacy endpoints include: focal aware seizures without motor features (eg, absence or focal nonmotor seizures with or without impairment of awareness), infantile or epileptic spasms, and myoclonic seizures.

Baseline for efficacy assessments is defined as based on the participant's prior study as follows:

- Study 1042-TSC-2001 – the original 4-week screening period for participants continuing in Study 1042 TSC-3002
- Study 1042-TSC-3001 – the original 4-week screening period for participants previously randomized to GNX.

Post-baseline 28-day seizure frequency will be calculated as the total number of seizures in the open-label phase divided by the number of days with seizure data in the same period, multiplied by 28. Baseline 28-day seizure frequency will be calculated as the total number of seizures in the baseline phase divided by the number of days with seizure data in the same period, multiplied by 28. The calculation for percent change from baseline in 28-day seizure frequency will be done as follows for each participant:

$$\left( \frac{[(\text{Post-baseline 28-day seizure frequency}) - (\text{Baseline 28-day seizure frequency})]}{(\text{Baseline 28-day seizure frequency})} \right) \times 100\%$$

The baseline, post-baseline, and arithmetic and percent changes from baseline in 28-day seizure frequency will be summarized using descriptive statistics. The following subgroup summarizations will be also applied:

- Gender (Female vs Male).
- Age groups (1 to 6 years; 7 to 12 years; 13 to 17 years; and 18 years and above).

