#### **4.4.2. Number (%) of participants considered treatment responders**

The number and percentage of subjects experiencing a reduction (improvement) of at least 50% from baseline in the 28-day seizure frequency of the primary seizure types will be summarized. In addition, a cumulative responder curve figure will be provided, in which the X-axis represents amount of improvement in increments of 5%, and the Y-axis represents the percentage of subjects improving by at least the amount on the X-axis. The treatment groups will be presented separately within the figure. Subgroup summaries for gender and age groups listed in section 4.4.1 will be also applied.

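### The primary objective names children and adults, but no AE or SAE table is pre-specified by age; only the C-SSRS and the developmental examination are reported by age

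*Protocol*

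**What the plan says.** Protocol section 3 gives the primary objective as "To assess the long-term safety and tolerability of GNX as adjunctive therapy for seizures associated with TSC in children and adults", and SAP 2.2.1 repeats it. The primary endpoints are all safety endpoints: AEs, SAEs, withdrawals and dose reductions due to AEs; vital signs; physical, neurological and developmental examination; ECG; laboratory tests; and the C-SSRS.

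Age enters the planned summaries as follows.

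- **Efficacy.** Protocol 9.2.6 defines four bands (1–6, 7–12, 13–17, and 18 and above) under the sentence "The following subgroup summarizations of the efficacy parameter are planned as outlined in the SAP". SAP 4.4.1 attaches them to 28-day seizure frequency ("The following subgroup summarizations will be also applied") and SAP 4.4.2 to responders ("Subgroup summaries for gender and age groups listed in section 4.4.1 will be also applied"). Both endpoints are secondary.
- **Safety, general.** Protocol 9.2.5 stratifies safety results overall and by parent-study treatment, and leaves the detail to the SAP.
- **Adverse events.** SAP 4.3.1 says "For the safety Analysis Set, the following tabular summaries will be created" and lists ten TEAE summaries. None is by age.
- **Other safety data.** The laboratory, vital-sign, physical, neurological and ECG summaries (SAP 4.3.2 to 4.3.4) carry no age split.
- **Two exceptions.** SAP 4.3.5 states "Adult and pediatric C-SSRS data will be summarized separately", and SAP 4.3.3 summarizes developmental findings in pediatric patients only.
- **Demographics.** SAP 5.3 already defines a 17-and-under versus over-17 grouping, for baseline description.

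**The concern.** The objective asks about two populations, and the tables that carry most of the answer report one mixture of them. If children and adults have different rates of, say, somnolence, the pooled percentage describes neither group. The plan would then report a secondary efficacy endpoint by age but not the primary AE endpoint.

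Different rates are plausible on the documents' own account. Protocol 2.2.2.2 says CNS events appeared to be dose related. Protocol 6.2 and 9.2.5 give the daily ceilings as 63 mg/kg or 1800 mg, which coincide at 1800/63 = 28.6 kg. A participant of that weight at the ceiling receives 63 mg/kg/day. An adult at 1800 mg/day receives 36.0, 25.7 or 20.0 mg/kg/day at an assumed weight of 50, 70 or 90 kg. Below 28.6 kg the absolute daily amount is smaller. The documents do not say which way this would move event rates, and pooled tables would not reveal it.

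**Working it through.** The plan gives no event rate, alpha or power for safety, so it has no figure to reproduce. The check has three steps.

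**1. Which primary safety summaries are by age?**

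| Primary component | Place | Age-specific summary? |
|---|---|---|
| TEAEs and SAEs (ten tables) | SAP 4.3.1 | No |
| Laboratory | SAP 4.3.2 | No |
| Vital signs | SAP 4.3.3 | No |
| Physical and neurological examination | SAP 4.3.3 | No |
| Developmental examination | SAP 4.3.3 | Pediatric only |
| ECG | SAP 4.3.4 | No |
| C-SSRS | SAP 4.3.5 | Adult and pediatric separately |

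SAP 4.1 refers to a subgroup when it defines the at-risk denominator for AEs, but no section defines a safety subgroup. SAP section 6 records no departure from the protocol's analyses that would fill the gap.

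**2. What a pooled rate can tell.** Let *s* be the pediatric share, *c* the rate in children and *a* the rate in adults. The pooled rate is *s·c* + (1 − *s*)·*a*: one equation with two unknowns, even when *s* is known. The documents give neither the share nor age-specific rates, so all values below are assumed.

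| *s* | *c* = 30%, *a* = 10% | *c* = 10%, *a* = 30% |
|---|---|---|
| 0.3 | 0.09 + 0.07 = 16% | 0.03 + 0.21 = 24% |
| 0.5 | 0.15 + 0.05 = 20% | 0.05 + 0.15 = 20% |
| 0.7 | 0.21 + 0.03 = 24% | 0.07 + 0.09 = 16% |

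At an equal split, two opposite safety profiles produce the same table entry.

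**3. Would a child/adult split be informative?** Inputs are *N* = 169 (protocol 9.4) or 150 (SAP 3.1), the same assumed shares, and *n* = *s·N* rounded. The exact one-sided 95% upper bound after zero events is 1 − 0.05^(1/*n*). The chance of seeing at least one case of a 1% event is 1 − 0.99^*n*.

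| *N* | Share | Children | Bound after zero events | Chance of ≥1 case at 1% |
|---|---|---|---|---|
| 169 | 30% | 51 | 5.7% | 40% |
| 169 | 50% | 84 | 3.5% | 57% |
| 169 | 70% | 118 | 2.5% | 70% |
| 150 | 30% | 45 | 6.4% | 36% |
| 150 | 50% | 75 | 3.9% | 53% |
| 150 | 70% | 105 | 2.8% | 65% |

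For comparison, the bound for everyone pooled is 1.8% at 169 and 2.0% at 150. If the children at *N* = 169 divided equally over the three pediatric bands (assumed), each band would hold about 17, 28 or 39, with zero-event bounds of 16.2%, 10.1% or 7.4%. The two-way split is usable descriptively; the three pediatric bands are imprecise.

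**The case against.** The other side has several fair points.

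- **Age is not absent from safety.** A reader of protocol 9.2.6 might infer that age is considered for efficacy alone. That is true of the four bands only. The C-SSRS and the developmental examination are primary endpoints with age-specific summaries. The latter is an examination done only in children rather than a split of a shared endpoint, but it is still reported for children.
- **Children's data are not lost.** A reader might go further and infer that the study cannot show safety in children. The documents do not support that: by-patient listings are planned for AEs, laboratory values, vital signs and ECGs. What is missing is a pre-specified aggregate.
- **Pooling normal ranges matters less than it seems.** Laboratory shift tables use reference-range classes, several measures are summarized as change from baseline, and examination and ECG findings are judged patient by patient. This weakens the case for splitting those summaries, though not for raw means. A 1-to-17 group would itself still mix normal ranges.
- **The table shells are a separate document** and might contain age splits. That cannot be checked here, and neither the protocol nor the SAP asks for them.
- **The study is descriptive.** SAP 3.2 applies no multiplicity control, and SAP section 6 allows later amendment or additional analyses, so the tables could be added afterwards. That stands, but it shows equally that specifying them now costs little.

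**Conclusion.** The point holds in a limited form. Outside the C-SSRS and the developmental examination, no primary safety summary is pre-specified by age, so the planned tables yield no aggregate AE or SAE rate for either population named in the objective. This is an inexpensive improvement to the primary analysis, not a flaw that invalidates it.

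The effect on any particular rate cannot be sized from the documents; the pooling figures only show that the pooled table does not identify the two rates. The precision figures rest on assumed pediatric shares of 30 to 70% and on the planned enrollment, which differs between protocol and SAP. The range 1 to 65 years is the widest parent-study entry range, not an age limit of the extension, so participants may be older while on study.

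**What to change.** 1. Extend protocol 9.2.6 to the safety endpoints.
2. In SAP 4.3.1, repeat the TEAE overview, TEAEs by SOC and preferred term, related TEAEs and serious TEAEs for 17 and under versus over 17 years, the grouping already in SAP 5.3. Show exposure (SAP 5.7) by the same groups so that rates can be read against time on drug.
3. State the date at which age is taken, since a participant can pass 18 during about three years of treatment.
4. As support, summarize vital signs and other continuous safety values by the same split.
5. Keep the four bands optional and for the TEAE overview only, given the likely small cells.

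The cost is programming and more tables. No new data, sample-size change or alpha is involved. The downside is limited precision, especially in the youngest band, so small cells should be read as description and not as evidence that a risk is absent.
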